## 6. Data management and statistical analysis

### 6.1 Statistical Software

Data statistics are processed by biostatisticians using the statistical software SPSS 20.0.

### 6.2 Data description

The measurement data are described as mean standard

deviation ( $\bar{x} \pm s$ ), median, maximum, minimum, and quartiles, and the count data are expressed as percentages (%).

### **6.3 Statistics**

Data entry: Enter the age, gender, kidney cancer stage and prognosis follow-up of the subjects.

Data management: The data are presented by number, and all personnel except the initial data entry personnel do not have access to the subjects' initial information (including subjects' personal information such as subjects' names, addresses, occupations and other sensitive information). There is no direct contact between the data entry personnel and the subjects, and all privacy of the subjects is protected from disclosure.

All hypothesis tests are two-sided, and differences are considered statistically significant at  $P < 0.05$ . Baseline data are evaluated for comparability between groups, and two-tailed statistical tests are performed at the  $\alpha=5\%$  level. The chi-square test or Fisher's exact probability method is used for comparison between groups for count data, the t-test for comparison between groups for measurement data, and the rank sum test for comparison between groups for nonparametric variables.

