## 4. Study population

### 4.1 Inclusion criteria

1. The age is between 18 and 80 years old.
2. Stage T1a or T1b according to the 8th edition of the AJCC TNM staging of kidney cancer, 2017.
3. The patients who underwent PN or TE between 2014 and 2022.

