## **5. Experimental program**

**5.1** The patients are screened according to the inclusion and exclusion criteria. Then the patients are divided into two groups according to whether they underwent zero-ischemic enucleation or partial nephrectomy, with the zero-ischemic enucleation group as the test group and the partial nephrectomy group as the control group. Describing the preoperative conditions (age, sex, Anatomy of tumor, RENAL score, ABC score, preoperative renal function), the perioperative conditions (operation time, intraoperative bleeding, perioperative complications, negative/positive specimen margins, postoperative renal function changes, postoperative hospitalization days), and the postoperative condition (follow-up renal function, tumor recurrence rate, overall survival, tumor-free survival, progression-free survival).

**5.2** The data of the two groups are corrected for baseline and screened so that there is no statistical difference in the number of patients, gender age, tumor anatomy, renal function and other preoperative conditions between the two groups (t-test/rank sum test  $p > 0.05$ ).

**5.3** The zero ischemic renal enucleation group is grouped according to RENAL score, ABC score and other scoring criteria. Different preoperative tumor score groupings are used as exposure

factors, and the percentage decrease of postoperative renal function compared with preoperative, perioperative complication rate and postoperative survival rate are used as outcome variables to analyze the association between exposure factors and outcome, to investigate the association of different factors on the surgical outcome of zero ischemic renal enucleation.

**5.4** Using zero-ischemic nephrectomy or partial nephrectomy with clamping of the renal hilum as the exposure factor. T-test/rank sum test and one-way regression are used to compare the efficacy indexes such as negative/positive tumor margins, postoperative and follow-up renal function, survival rate, and safety indexes such as perioperative complication rate and intraoperative bleeding between the two groups to investigate whether there is a statistical difference in their treatment safety and efficacy. Then we investigated whether there are statistical differences and correlations between the safety and efficacy of the treatment, and whether there are statistical differences in survival outcomes between the two groups by multifactorial cox regression.

[figure not shown]

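### Section 5.4 compares renal function, margins, complications and bleeding without adjusting for T1a/T1b stage, and the p > 0.05 baseline screen in 5.2 is too weak to make up for it

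*Combined protocol and SAP*

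**What the plan says.** All references are to the combined protocol and SAP.

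- **Eligibility.** Section 4.1 admits "Stage T1a or T1b according to the 8th edition of the AJCC TNM staging of kidney cancer, 2017". Both stages can therefore occur in either group.
- **Data entry.** Section 6.3 tells staff to "Enter the age, gender, kidney cancer stage and prognosis follow-up of the subjects".
- **Preoperative description.** Section 5.1 lists "age, sex, Anatomy of tumor, RENAL score, ABC score, preoperative renal function". Stage is not in the list.
- **Balancing.** Section 5.2 states: "The data of the two groups are corrected for baseline and screened so that there is no statistical difference in the number of patients". It goes on to cover "gender age, tumor anatomy, renal function and other preoperative conditions between the two groups", with p > 0.05 by t-test or rank sum test as the criterion. Stage is not named, but the wording is open-ended.
- **Group comparison.** In section 5.4, "T-test/rank sum test and one-way regression are used to compare the efficacy indexes" (margins, renal function, survival rate) and the safety indexes (complications, bleeding). For survival it also looks for "statistical differences in survival outcomes between the two groups by multifactorial cox regression". No covariate is named for any of these.
- **General baseline check.** Section 6.3 says that baseline comparability will be evaluated. It lists no variables and does not say what follows if the groups differ.

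**The concern.** The study is retrospective, and the groups are defined by the operation performed. Section 1 describes enucleation as technically harder than conventional partial nephrectomy, so it is plausible that tumour features influenced the choice of operation. Larger tumours plausibly also mean more parenchyma lost, more bleeding and more complications. A factor linked to both the choice and the outcome confounds the comparison.

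Two steps could protect against this: balancing in 5.2 and adjustment in 5.4. For the non-survival outcomes 5.4 has no adjustment, so any stage difference left after 5.2 passes directly into the contrast between operations. The question is how large a difference 5.2 can leave.

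**Working it through.** **Inputs from the documents.** 73 patients per group (section 3); two-sided 5% level, with chi-square or Fisher's exact test for count data (6.3); p > 0.05 as the balance criterion (5.2).

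**Inputs assumed.** The T1b share in each group, and the effect of T1b on the outcome. The documents give neither, so ranges are shown.

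**The plan's own figure.** The 73 per group cannot be reproduced, because section 3 gives no values for the two event rates or the power. Several input sets give it, for example 35% v 15% at 80% power, two-sided. The point does not depend on this; 73 is used only as the group size.

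**Step 1: one worked example.** Take 20/73 (27.4%) v 31/73 (42.5%) T1b tumours.

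- Difference = 11/73 = 0.151.
- Pooled share = 51/146 = 0.349.
- Standard error = √(0.349 × 0.651 × 2/73) = 0.0789.
- z = 0.151/0.0789 = 1.91, so p = 0.056 (uncorrected chi-square). Fisher's exact test gives 0.082, and the rank sum test without continuity correction gives 0.057.

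The groups pass. With 32 instead of 31, p = 0.038 by uncorrected chi-square and they fail.

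The standardised difference for 20 v 31 is 0.151/√[(0.274 × 0.726 + 0.425 × 0.575)/2] = 0.151/0.471 = 0.32.

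**Step 2: largest gap that still gives p > 0.05, by T1b share.**

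| T1b in one group (of 73) | Largest T1b count in the other, chi-square | Gap (points) | p | Largest count, Fisher | Gap (points) |
|---|---|---|---|---|---|
| 7 | 15 | 11.0 | 0.064 | 16 | 12.3 |
| 15 | 25 | 13.7 | 0.064 | 26 | 15.1 |
| 22 | 33 | 15.1 | 0.060 | 34 | 16.4 |
| 29 | 40 | 15.1 | 0.068 | 41 | 16.4 |
| 36 | 47 | 15.1 | 0.066 | 48 | 16.4 |

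The screen, if applied to stage, therefore tolerates about 11 to 16 points. If it is not applied to stage, 5.2 sets no direct limit.

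**Step 3: carry the gap into the outcome.** Suppose the operation has no effect and the stage effect is the same in both groups. The expected unadjusted difference is then the gap in T1b share × the T1b effect.

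- GFR loss, T1b effect assumed 5 to 15 points: from 0.110 × 5 = 0.55 to 0.151 × 15 = 2.27 points, using the chi-square limits. Fisher's widest gap would raise the top to 0.164 × 15 = 2.46.
- Complications, T1b effect assumed 10 to 20 points, 15.1-point gap: 0.151 × 10 = 1.5 to 0.151 × 20 = 3.0 points.
- Survival, if stage is left out of the Cox model: with an assumed stage hazard ratio h and T1b shares a and b, the crude ratio is approximately (1 − b + bh)/(1 − a + ah). Over the chi-square limits, with h from 2 to 4, this is 1.10 to 1.26.

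**The case against.** The strongest reply is that stage is unnamed rather than excluded. Section 5.2 covers tumour anatomy and ends with an open reference to other preoperative conditions. Section 6.3 evaluates baseline data and lists stage for entry in the same section. It is fair to read stage into either, so one cannot infer that the plan leaves stage out of balancing altogether. This does not remove the problem, because the working shows what the screen allows even when stage is included. It also means that simply adding stage to the 5.2 list would leave the same gap.

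Other parts of the reply also stand:

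- The sizes are near-worst cases. They take the largest imbalance that passes and treat stage as separate from tumour anatomy. Balancing anatomy, and excluding tumours near the collecting system or touching the renal vessels (4.2, item 3), plausibly narrows the gap.
- The survival model is already multivariable, and section 3 mentions multi-factor regression. Stage could enter either, though no covariates are named.
- The plan states no margin against which a bias of 1 or 2 GFR points could be called decisive.

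A reader might also infer that the zero-ischemia group has more T1a tumours, so that every comparison in 5.4 favours it. The documents give no stage split by group, so neither the imbalance nor its direction is shown. Nor do they support the inference that a benefit confined to T1a would be reported as holding for all T1 tumours; nothing in them indicates that the effect differs by stage.

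**Conclusion.** The concern holds as a weakness in the planned analysis, not as a demonstrated bias. Followed as written, 5.4 leaves any residual stage difference in the unadjusted contrasts for renal function, margins, complications and bleeding, although stage is already entered. The 5.2 screen can pass a T1b gap of about 11 to 16 points at 73 per group. Under the assumed T1b effect of 5 to 15 points, that corresponds to roughly 0.6 to 2.3 points of apparent GFR-loss difference (chi-square limits), in an unknown direction. The figures rest on assumed T1b shares, an assumed stage effect common to both groups, and no reduction from balancing anatomy. The change is worth making because the bias is plausible and the adjustment is cheap.

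**What to change.** 1. In 5.4, replace the one-way comparisons of renal function, complications and bleeding with multivariable regressions that include operation and T1a/T1b (or tumour size), as far as event numbers allow.
2. Name stage as a covariate or stratum in the Cox model already planned.
3. Report the T1b share in each group with its standardised difference, and do not take p > 0.05 as evidence of balance.
4. State whether stage is clinical or pathological, which the documents leave open. If it is pathological it is not a preoperative variable, and preoperative tumour size may be the better covariate.

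The cost is slightly more analysis work: a model replaces a two-group test for each of these outcomes. Stage needs no new data item; tumour size may need extraction, since it is not listed separately. Sparse outcomes are the main limit. Section 1 reports no positive margins and no local recurrence in more than 500 of the team's enucleations, so margins may support only a descriptive display by stage, and the Cox model may support few covariates. The covariate should be fixed before the outcomes are analysed, so that it is not chosen after the results are seen.

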## **7. Informed consent**

Previous case information is used for this study and a waiver of informed consent is requested.
